4.2 Registration Eligibility

- 4.2.1** Successful completion of three 24-hour dietary recalls during the run-in period.
- 4.2.2** Patients consuming ≥ 6 servings per day of fruits and vegetables (not including juices), as determined by the run-in dietary recalls are not eligible.

5.0 REGISTRATION

Informed Consent: The patient must be aware of the neoplastic nature of his disease and willingly consent after being informed of the procedure to be followed, the experimental nature of the study, alternatives, potential benefits, side effects, risks and discomforts.

Protected Health Information: In order to contact patients by telephone and by mail, it will be necessary to collect those participants' names, addresses, and telephone numbers. This information will be sent to the University of California, San Diego Moores Cancer Center and will be destroyed upon completion of the study.

5.1 CTSU registration requirements

This study is supported by the NCI Cancer Trials Support Unit (CTSU).

Prior to the recruitment of a patient for this study, investigators must be registered members of a Cooperative Group. Each investigator must have an NCI investigator number and must maintain an "active" investigator registration status through the annual submission of a complete investigator registration packet (FDA Form 1572 with original signature, current CV, Supplemental Investigator Data Form with signature, and Financial Disclosure Form with original signature) to the Pharmaceutical Management

Branch, CTEP, DCTD, NCI. These forms are available on the CTSU Web site (enter credentials at <https://www.ctsuo.org>; then click on the Register tab) or by calling the PMB at [REDACTED] Monday through Friday between 8:30 a.m. and 4:30 p.m. Eastern time.

Each investigator or group of investigators at a clinical site must obtain IRB approval for this protocol and submit IRB approval and supporting documentation to the CTSU Regulatory Office before they can enroll patients. Study centers can check the status of their registration packets by querying the Regulatory Support System (RSS) site registration status page of the CTSU member web site by entering credentials at <https://www.ctsuo.org>.

Requirements for CALGB 70807 site registration:

- CTSU IRB Certification
- CTSU IRB/Regulatory Approval Transmittal Sheet

5.2 Patient Pre-registration

Pre-registration must occur prior to providing patients with access to the online patient data entry site, login information or training. Pre-registration to the optional companion studies will be performed at the time pre-registration occurs to the intervention study.

All site staff (Lead Group and CTSU Sites) will use OPEN to enroll patients to this study. OPEN can be accessed at <https://open.ctsuo.org> or from the OPEN tab on the CTSU members' side of the website at <https://www.ctsuo.org>.

Prior to accessing OPEN site staff should verify the following:

- All eligibility criteria have been met within the protocol stated timeframes. Site staff should use the OPEN Enrollment forms provided on the group or CTSU web site as a tool to verify eligibility.
- All patients have signed an appropriate consent form and HIPAA authorization form (if applicable).

Access requirements for OPEN:

- Site staff will need to be registered with CTEP and have a valid and active CTEP-IAM account. This is the same account (user id and password) used for the CTSU members' web site.
- To perform registrations, the site user must have been assigned the 'Registrar' role on the relevant Group or CTSU roster.
- To perform registrations on protocols for which you are a member of the Lead Group, you must have an equivalent 'Registrar' role on the Lead Group roster. Role assignments are handled through the Groups in which you are a member
- To perform registrations to trials accessed via the CTSU mechanism (i.e., non-Lead Group registrations) you must have the role of Registrar on the CTSU roster. Site and/or Data Administrators can manage CTSU roster roles via the new Site Roles maintenance feature under RSS on the CTSU members' web site. This will allow them to assign staff the "Registrar" role.

The OPEN system will provide the site with a printable confirmation of pre-registration. Please print this confirmation for your records.

Further instructional information is provided on the OPEN tab of the CTSU members' side of the CTSU website at <https://www.ctsuo.org> or at <https://open.ctsuo.org>. For any additional questions contact the CTSU Help Desk at [REDACTED].

Within 24 hours of receiving the Confirmation of Preregistration, fax the C-2010, MEAL Participant Contact Information Form to Nutrition Shared Resource at UCSD at [REDACTED] and notify [REDACTED] via email at [REDACTED].

5.3 Preregistration to companion study 151105

There is one substudy within CALGB 70807. This substudy must be offered to all patients enrolled on CALGB 70807 (although patients may opt not to participate). The substudy included within CALGB 70807 is CALGB 151105, “Carotenoid and polymorphism analysis of patients enrolled to CALGB 70807.” This study does not require separate IRB approval.

If a patient answers “yes” to “I agree that my specimens may be used for the research described above,” (Question #1) in the Model Consent, he has consented to participate in the correlative science studies described in Sections 10.2, 10.3, and 10.4. The patient should be pre-registered to CALGB 151105 at the same time that he is pre-registered to CALGB 70807 and in addition to collecting the required plasma for carotenoid and cholesterol testing; whole blood, serum, and unstained slides should be collected per Section 6.2. Whole blood samples should be submitted at the time of pre-registration.

5.4 Run-In

Within one week of receiving the C-2010, MEAL Participant Contact Information Form from sites, patients will be called by the nutrition unit at UCSD on randomly selected days to complete three 24-hour dietary recalls. The series of dietary recalls will be completed within 2-3 weeks. Participants will have two chances to successfully complete the run-in.

5.5 Patient Registration/Randomization

Upon completion of the run-in, UCSD staff will notify the site and the study Data Coordinator about patient eligibility. Eligible patients who completed the run-in and consumed fewer than 6 servings of fruit and vegetables per day will then be registered and randomized by the site. Patients who are determined to be ineligible for the study should be notified by participating institution staff.

Registration procedures:

- Site staff will need to be registered with CTEP and have a valid and active CTEP-IAM account. This is the same account (user id and password) used for the CTSU members' web site.
- To perform registrations, the site user must have been assigned the 'Registrar' role on the relevant Group or CTSU roster.

The OPEN system will provide the site with a printable confirmation of registration. Please print this confirmation for your records.

Once the randomization is complete, patients will be contacted by UCSD staff for their initial orientation telephone call. Patients will also receive an enrollment packet, provided by UCSD, which will contain the informational materials described in Section 8.3.

5.6 Registration to companion study 151105

If a patient answered “yes” to “I agree that my specimens may be used for the research studies described above.” (Question #1) in the Model Consent, the patient should have been pre-registered to CALGB 151105 at the same time that he was pre-registered to 70807. At this time, patients who were pre-registered to 151105 should be registered to the study and samples submitted per Section 6.2.

5.7 Stratification Factors

1. Age
 - a) Men ≤ 70 years
 - b) Men > 70 years
2. Race
 - a) Black or African American
 - b) Other
3. Baseline Prostate Biopsy
 - a) 0-12 months prior to pre-registration
 - b) > 12-24 months prior to pre-registration

6.0 DATA SUBMISSION AND SAMPLE SUBMISSION

6.1 Data Submission

Forms should be submitted to the Alliance Statistics and Data Center (SDC) in compliance with the Data Submission Schedule below.

Forms must be submitted electronically using the “Submit to CALGB” button located at the bottom of the last page of each form. Any required forms, supporting documentation or amended forms that cannot be submitted electronically should be mailed directly to the Alliance Data Center for scanning and quality review at the address below:

Alliance Data Center

[Redacted address information]

For the most up-to-date forms, please visit the Alliance or CTSU web site.

Data Submission Schedule:

Form		Submission Schedule
	Pre-Registration Pre-Registration Worksheet	Submit at pre-registration
C-2010	MEAL Participant Contact Information Form	Submit to UCSD staff (See Sec. 5.2)
	Registration Registration Worksheet CALGB 70807 On Study Form	Submit within 2 weeks of registration
C-2002	CALGB 70807 Personal Habits Questionnaire	To be administered to patients at the pre-registration visit and submitted to the Alliance Statistics and Data Center within 2 weeks of registration.
C-2003	CALGB 70807 MAX-PC Form	
C-2004	CALGB 70807 Nutritional Self Efficacy Form	
C-2005	CALGB 70807 IPSS Form	
C-2023	CALGB 70807 EPIC-26 Form	
C-2007	CALGB 70807 FACT-P Form	
	During Intervention	
C-2013	CALGB 70807 Follow Up Form	Submit at 3, 6, 9, 12, 15, 18, 21, 24 months
C-2081	CALGB 70807 PSA Doubling Time Form	Submit at 6 months
C-2003	CALGB 70807 MAX-PC Form	Submit at 6, 12, 18 and 24 months
C-2005	CALGB 70807 I-PSS Form	
C-2023	CALGB 70807 EPIC-26 Form	
C-2007	CALGB 70807 FACT-P Form	
C-2004	CALGB 70807 Nutritional Self Efficacy Form	
C-2008	CALGB 70807 MEAL Study Counseling Evaluation Form	Arm A patients only: Submit at 12 and 24 months
	Post Intervention Follow-Up	
C-2013	CALGB 70807 Follow Up Form	Submit every 3 months until 2 years from date of registration (see Section 8.7)
	Other	
C-260	CALGB Remarks Addenda	Submit as needed

If a study participant chooses to withdraw from the study, submit the C-260 CALGB Remarks Addenda to the Alliance Data Center and copy by fax [REDACTED]

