8.0 INTERVENTION

The principal strategy to promote dietary change in the intervention arm will be a telephone counseling protocol with individualized, one-on-one assistance tailored to each participant. The intervention will last 24 months. Intervention participants will engage in a series of telephone-based diet counseling sessions throughout the study. The first phase of sessions will guide initial diet-change attempts, the second will help participants complete their diet changes, and the third and fourth phases will enable participants to maintain and monitor their diet changes. This highly structured, computer-assisted telephone counseling protocol will facilitate standardization of the intervention.

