8.7 Completion of Intervention

All patients are expected to participate in the diet intervention for 24 months.

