8.7.1 Off Treatment Criteria

Off-Treatment criteria will include the following: 1) physician determination that continuation of the diet is medically contraindicated, 2) participant decision to withdraw from the dietary intervention, or 3) participant death. If a study participant chooses to withdraw from the study, submit the C-260 CALGB Remarks Addenda to the Alliance Data Center and copy by fax [REDACTED]

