8.7.3 Continuation of the Dietary Intervention

Patients should continue intervention and follow-up for the two-year duration of the study regardless of progression or electing to receive therapy.

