Time to Treatment: Probability to proceed to treatment within 2 years (binary observation) and time to treatment (censored time to an event observation) will be analyzed using the chi-squared test and the log-rank test, respectively. We expect that the control arm will have more patients receiving treatment and shorter time to treatment than the experimental arm because of anxiety.

QOL: Quality of life (anxiety and depression, prostate cancer symptom checklist) will be compared between the two arms. The time trajectory of QOL will be estimated using the generalized estimating equation method based on working independent correlation structure (103) and the slope of the time trajectory will be compared between the two arms (104). We will consider taking a log-transformation of QOL observations if it improves the linearity of the time trajectory of QOL. The significance of the two arm comparisons will be adjusted for multiple testing among different QOL subscales using the methodology of Bang, Jung and George (105).

Dietary Recall: Diets will be evaluated at baseline and at 12 and 24 months by a series of three separate 24-hour dietary recalls collected interactively via telephone interview. The increase (from baseline) in mean daily intakes of total vegetables, crucifers, tomato products, beans/legumes and fat will be compared between arms using a two-sample t-test at 12 and 24 months. We may consider transforming (e.g. using logarithm) the data to improve normality of the distributions and variance stabilization. Data will be catalogued and analyzed utilizing Minnesota Nutrition Data System (NDS) software (Nutrition Coordinating Center, University of Minnesota).

Plasma carotenoid analyses:

- (1) Plasma carotenoid concentrations (PCC) will be compared between the two arms using a two-sample t-test. A log-transformation of the PCC observations may be considered in order to improve the normality of the distributions and variance stabilization.
- (2) PCC will be correlated with PSADT for the patients. Descriptive analysis using scatter plots and regression analysis will be conducted. Intervention and known predictors including the stratification factors will be adjusted in multivariable analysis.

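### Section 6.1 drops the anxiety and quality-of-life forms once a man leaves the intervention, Sections 7.0 and 8.4 keep them to month 24, and any resulting data loss would fall mainly on Arm A

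*Combined protocol and SAP*

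**What the plan says.** **Section 6.1, Data Submission.** Sites are told to follow a schedule with two states after registration.

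- *During Intervention* lists C-2013 (Follow Up Form) every three months. It also lists MAX-PC, I-PSS, EPIC-26 and FACT-P with the instruction "Submit at 6, 12, 18 and 24 months".
- *Post Intervention Follow-Up* lists C-2013 alone: "Submit every 3 months until 2 years from date of registration (see Section 8.7".

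**Length of the intervention.** Section 8.0 states: "The intervention will last 24 months". Section 8.7, to which the post-intervention row points, says: "All patients are expected to participate in the diet intervention for 24 months".

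**Coming off the intervention (8.7.1).** Apart from death, there are two reasons: "physician determination that continuation of the diet is medically contraindicated" and "participant decision to withdraw from the dietary intervention". The section does not say which assessments continue afterwards. Its next sentence concerns leaving the study, which is recorded on form C-260.

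**Continuation (8.7.3).** "Patients should continue intervention and follow-up for the two-year duration of the study regardless of progression or electing to receive therapy". Stopping the diet is not mentioned.

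**The other schedules.** The Section 7.0 calendar marks the four instruments at months 6, 12, 18 and 24, with visits timed from randomization and no off-diet exception. Section 8.4 sets the questionnaires every six months, also without reference to diet status.

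**Analysis (11.3, QOL).** "The time trajectory of QOL will be estimated using the generalized estimating equation method based on working independent correlation structure", after which the slopes are compared between arms. No method for missing data is stated.

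**The concern.** Sites hold two instructions that disagree for a man who has stopped the diet. Under 6.1 he has moved to a state in which only C-2013 is due. Under 7.0 and 8.4 his questionnaires are still due every six months. Section 8.7, the cross-reference, does not settle it. A questionnaire not completed at its visit cannot be recovered later.

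The arms are not equally exposed. Counseling is for Arm A only (8.6), and Arm B receives printed information and newsletters. The two off-treatment reasons other than death both presuppose a diet to stop.

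Secondary objectives 2.2.2 (anxiety) and 2.2.3 (health-related quality of life) are at stake. An unweighted GEE with working independence uses whatever visits are available. In general it is safe only when missingness is unrelated to the scores, given the covariates in the model. The protocol gives some reason to doubt that for men who stop: Sections 1.6 and 8.6 treat falling self-efficacy as a warning of failure or relapse, and Section 1.5 links self-efficacy to quality of life.

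**Working it through.** The plan gives no figure on this point to reproduce. The check is first a comparison of the sections, then an illustration of scale.

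**1. Whom can the post-intervention row cover?** The intervention lasts 24 months (8.0, 8.7). The row ends 2 years from registration (6.1), and registration and randomization are a single step (5.5). A man who completes the intervention therefore has no post-intervention time before the row expires. In practice the row can apply only to men who leave early.

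**2. What is due for a man who stops the diet at, say, month 9?**

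| Source | Four instruments at months 12, 18, 24 |
|---|---|
| 6.1, read literally | Not listed; C-2013 only |
| 7.0 calendar | Due, timed from randomization |
| 8.4 | Due every six months |
| 8.7.1 | Silent |
| 8.7.3 | Covers progression and elected therapy; silent on stopping the diet |

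**3. What would be lost?** Only visits after stopping. Baseline forms and forms completed before stopping remain, and they enter the GEE.

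**4. Illustration of scale.** The share of Arm A men who stop early, *s*, and the difference in later scores between continuers and stoppers, *d*, are not in the documents. Assume *s* = 10-20% and *d* = 0.3-0.5 SD.

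If continuers have mean *m* and stoppers *m* − *d*, the full Arm A mean is *m* − *s·d*, while the observed mean is *m*. The shift is *s·d*.

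- Low corner: 0.10 × 0.3 = 0.03 SD, with about 0.10 × 232 = 23 men lacking the form.
- High corner: 0.20 × 0.5 = 0.10 SD, with about 0.20 × 232 = 46 men lacking the form.

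For comparison, the standard error of a two-arm difference in means at one visit is:

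- all 232 per arm: √(2/232) = 0.093 SD;
- 232 − 23 = 209 in Arm A: √(1/209 + 1/232) = 0.095 SD;
- 232 − 46 = 186 in Arm A: √(1/186 + 1/232) = 0.098 SD.

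The shift thus runs from about a third of a standard error (0.03/0.095) to about one (0.10/0.098). It does not shrink with sample size. These figures concern a mean at one visit where every stopper's form is missing. The planned test compares slopes, so they indicate scale and do not estimate the bias in that test.

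**5. Primary endpoint.** C-2013 appears every three months under both headings, so the omission does not reach time to progression.

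**The case against.** The strongest reply is that the plan already requires these forms. Section 7.0 is the list of required data, and it states exceptions where it means them: some forms are restricted to Arm A, and the 24-month biopsy is waived after definitive treatment. It makes no off-diet exception for the four instruments, and neither does 8.4. Nothing in 6.1 or 8.7 says outright that stopping the diet cancels the fixed-month questionnaires, and the post-intervention row may simply be a leftover. This stands in part. The documents contain a conflict between instructions, not a settled rule to stop collecting. But 6.1 is the schedule sites are told to follow when submitting forms, and it repeats C-2013 under the second heading without repeating the questionnaires.

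A reader might go further and infer the following, which the documents do not support:

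- *That the data will be missing in one arm only.* Section 6.1 applies its headings to both arms, 8.7 speaks of all patients, and death or study withdrawal can occur in either arm. A loss mainly in Arm A is a reasonable inference from 8.6 and 8.7.1, and no more than that.
- *That the analysis becomes all controls against Arm A adherers.* Stoppers still contribute their earlier visits.
- *That the bias favors the intervention.* No section reports anxiety or quality of life in men who stop this diet. The self-efficacy passages are general, and a man relieved of a demanding diet might score no worse.

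It can also be said that Section 9.6 calls these scores exploratory. Sections 2.2.2 and 2.2.3 nevertheless list anxiety and quality of life as secondary objectives.

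**Conclusion.** The inconsistency is real and should be corrected. Section 6.1 omits the four instruments after the intervention, Sections 7.0 and 8.4 require them to month 24, and 8.7.1 and 8.7.3 leave the man who stops the diet unaddressed. Sites that follow 6.1 literally may lose his later anxiety and quality-of-life forms, mainly in Arm A. With a working-independence GEE and no stated approach to missing data, the slope comparison could then be biased if stopping is related to outcome.

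Neither direction nor size can be taken from the documents. The illustrative shift of 0.03-0.10 SD at one visit rests on the assumed stopping rate and score difference, and on every site following 6.1 for every stopper. If sites work from the 7.0 calendar, this particular loss does not arise. The consequence is confined to secondary objectives 2.2.2 and 2.2.3.

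**What to change.** - **6.1:** Reconcile with 7.0 and 8.4. List MAX-PC, I-PSS, EPIC-26 and FACT-P for all patients in both arms at months 6, 12, 18 and 24 from randomization, whether or not the dietary intervention has been stopped.
- **8.7.3:** Add stopping the dietary intervention to the circumstances in which follow-up continues. Word it for assessments only, since the present sentence also covers continuing the intervention.
- **8.7.1:** State that assessments continue after a man stops the diet unless he withdraws from the study, in which case C-260 applies.

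The cost is rewording three sections and collecting a few questionnaires from men who have stopped counseling. Section 7.0 already schedules every one of them, so no form or visit is added and no clinical rule changes.

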6.2 Sample Collection and Submission

Histopathology review will be conducted using specimens from prostate biopsies. **The submission of these samples for histopathology review is required for all patients registered to this study.**

In addition, submission of plasma samples for carotenoid and cholesterol analyses is required for all patients registered to this study. Rationale and methods for the scientific components of these studies are described in Section 10.1.

Finally, all participating institutions must ask patients for their consent for the use of serum, whole blood, and unstained slides for the additional carotenoid and polymorphism analyses described in Sections 10.2, 10.3, and 10.4 (sub-study CALGB 151105).

Submit slides and blood samples as described below.

	Pre-registration*	12 months**	24 months**	Ship to:
	Required for all patients registered to 70807			
H&E slides	X		X	OSU
Plasma (Green top)	1 x 10 mL	1 x 10 mL	1 x 10 mL	OSU
	Required for patients registered to 70807 and substudy 151105			
Serum (Red top)	1 x 10 mL	1 x 10 mL	1 x 10 mL	OSU
Whole blood (Lavender top)	1 x 10 mL			OSU
Unstained slides	X			OSU

- Pre-registration samples should be submitted within two weeks after the patient has been registered and randomized to the study; except whole blood samples, which should be submitted on the same day as collection. If the patient does not complete the run-in, or is not registered/randomized to the study for any other reason, samples collected at pre-registration should be destroyed per institutional practice. The whole blood sample submitted at pre-registration will be destroyed by staff at the Alliance Biorepository at OSU.

** Blood samples should be collected and submitted regardless of whether the patient has progressed or elected to receive therapy. H & E slides at the 24-month time point are not required for patients who have started definitive treatment (e.g., prostatectomy or radiation therapy).

USE OF THE ALLIANCE BIOSPECIMEN MANAGEMENT SYSTEM (BioMS) IS MANDATORY AND ALL SPECIMENS MUST BE LOGGED AND SHIPPED VIA THIS SYSTEM.

BioMS is a web-based system for logging and tracking all biospecimens collected on Alliance trials. Authorized individuals may access BioMS at the following URL: <http://bioms.allianceforclinicaltrialsinoncology.org> using most standard web browsers (Safari, Firefox, Internet Explorer). For information on using the BioMS system, please refer to the 'Help' links on the BioMS web page to access the on-line user manual, FAQs, and training videos. To report technical problems, such as login issues or application errors, please contact: [REDACTED]. For assistance in using the application or questions or problems related to specific specimen logging, please contact: [REDACTED]

After logging collected specimens in BioMS, the system will create a shipping manifest. This shipping manifest must be printed and placed in the shipment container with the specimens.

All submitted specimens must be labeled with the protocol number (70807), patient study ID number, patient's initials and date and type of specimen collected (e.g., serum, whole blood). A copy of the Shipment Packing Slip produced by BioMS must be printed and placed in the shipment with the specimens.

Instructions for the collection of samples are included below. Please be sure to use a method of shipping that is secure and traceable. Extreme heat precautions should be taken when necessary.

Shipment on Monday through Friday by overnight service to assure receipt is encouraged. If shipping on Friday, FedEx or UPS must be used and the air bill must be marked "For Saturday delivery." Do not ship specimens on Saturdays.

All specimens should be sent to the following address:

Alliance Biorepository at Ohio State University
The Ohio State University
Innovation Centre

